6.2 INCLUSION CRITERIA

Phase 1 surveys, we will include consultant obstetricians, neonatologists, and midwives working in hospitals with neonatal intensive care units (as these are the only hospitals that will

deliver the extreme preterm births, which are included in the scenarios). We will also include members of the public recruited via partner organisations and Public Patient Involvement (PPI) group, PICTR (Patient involvement in Clinical trials research). This is a group of i volunteers who are interested in supporting and commenting on research projects. The Centre for Reproductive Health (Edinburgh) Clinical Obstetric Trial team manages the PICTR group.

Phase 2 consensus workshop, we will recruit clinicians (obstetricians, anaesthetists, midwives, nurses and neonatologists and midwives) with 5 years of more experience or providing clinical care to women at risk of preterm labour or preterm infants born.

For the consensus workshops and Delphi process we will include women and their partners who fulfill the following criteria:

- age greater than 16 years
- willing to consent
- previous experience of the following
 - i. Previous preterm labour or delivery
 - ii. Women at risk of future preterm labour or delivery

Phase 3 Qualitative interviews we will recruit clinicians (obstetricians, anaesthetists, midwives, nurses and neonatologists and midwives) with 5 years of more experience or providing clinical care to women at risk of preterm labour or preterm infants born using volunteers from phase 1 and 2.

For the focus groups, we will recruit women only who fulfill the following criteria:

- age greater than 16 years
- willing to consent
- previous experience of the following
 - i. Previous preterm labour or delivery
 - ii. Women at risk of future preterm labour or delivery

6.3 EXCLUSION CRITERIA

Phase 1, the survey

• We will exclude clinicians working in units without neonatal intensive care facilities

NB: Women and their partners who have experienced adverse events as a result of the issues

CASSAVA Version number 2 15th October 2018 IRAS ID 251310 above (e.g. neonatal death, stillbirth) will not be actively excluded from the consensus workshops or focus groups, but we will be mindful of the need to manage this sensitively. The members of the research team have significant experience of conducting mixed-methods research with parents who have experienced adverse events, including perinatal death.

7 CO-ENROLMENT

Co-enrolment will be allowed for this study as we are seeking the views and opinions of clinical staff and service users.

8 PARTICIPANT SELECTION AND ENROLMENT

8.1 IDENTIFYING PARTICIPANTS

8.1.1 Women and their partners

Four main strategies will be used to identify and approach women to participate in the interactive consensus workshop and in the focus groups.

(i) Some women will be invited to participate from antenatal clinics (including preterm birth clinics) and neonatal units at the NHS participating sites in Edinburgh, Bristol and London (UCL).

(ii) We will also recruit women and their partners through our charity partners Tommy and Bliss, the International Stillbirth Alliance, and the network of charities involved in the recent National Bereavement Care Pathway.

(iii) We will invite women who are already part of our PPI groups in Edinburgh, Bristol or London to participate.

(iv) Women from particular cultural groups: Polish (Edinburgh-based), Pakistani (Edinburghbased) and Indian (London-based) will be recruited local community groups using via bilingual researchers where necessary. Known and trusted community members will be the initial 'research brokers'. The (bilingual) researcher will hand out recruitment packs to women in community groups/settings and/or ask research brokers to distribute recruitment packs. Packs will contain an information sheet, an opt-in form and a consent form.

Examples of recruitment strategies (invitation letter for NHS sites and for our PPI group, adverts placed by our charity partners and information sheets and opt in forms for the cultural groups) are attached.

Women will be asked to involve their partner in the interactive workshop, but not the focus group. We anticipate that recruitment via NHS sites described in (i) above will need R&D

approval from those sites. We do not anticipate that recruitment of women through strategies (ii) – (iv) will need R&D approvals, since it does not involve the NHS.

8.1.2 Clinical health care experts

We will invite clinicians to participate in the survey, interactive working group and Delphi, and the qualitative interviews through our networks: Royal Colleges (Midwives, Nurses, Obstetricians, Neonatologists), preterm birth network, RCOG clinical study groups (preterm birth, stillbirth, intrapartum care), and British Maternal and Fetal Medicine Society members). With purposive sampling, we will aim to include clinicians (labour ward leads, midwifery and neonatal nurse leads, and neonatologist leads) where possible including those with diverging clinician views about optimal mode of delivery. We do not intend to approach any through their NHS trust, and so we do not anticipate that R&D approval will be required for clinician participated in the survey to additionally participate in the consensus working group and the interviews, but these second two events will be optional.

Other stakeholders, including healthcare regulators responsible for pregnancy and childbirth including NHS England, the Care Quality Commission, and National Institute for Health and Care Excellence will be invited to participate in the focus groups.

9 CONSENTING PARTICIPANTS

9.1 WOMEN (AND WHERE RELEVANT THEIR PARTNERS)

Women (and where relevant their partners) will be approached as described in section 6.4. They will be provided with an information sheet about the study. Those who wish to participate will complete a consent form. Consent for the interactive workshop will be taken by the study administrator (or other research staff). Potential participants who wish further information will be referred to the lead for the interactive consensus workshop ([name]) for further discussion.

Consent for the focus groups will be taken by the trained qualitative researcher conducting the focus groups. Those who wish further information will be referred to the lead for this part of the study, [name].

9.2 CLINICIANS

For the survey, clinicians will be approached by email – either directly (e.g. where we have consent from clinicians for contact for research related activities; where their email is publically available such as on NHS websites) or indirectly through Networks or societal email distribution lists. The email will describe the survey and its purpose, and include opt out options from further contact. The first email or advert will be followed by a second, follow-up email 2-7 days later, including further information and a link to the online survey for completion. A reminder email will be sent 6 weeks after initial approach. Consent will be presumed by survey completion. Potential participants who wish further information will be referred to [name] (lead for the survey) for further discussion.

Clinicians will be provided with an information sheet describing either the consensus workshop or the interview (as appropriate). They will be asked to complete a consent form for the relevant part of the study. Most of this will be done by post. Potential participants who wish further information will be referred to the lead for the relevant part of the study ([name] for the survey, [name], for the interactive consensus workshop or the qualitative researcher or [name] for the interviews) for further discussion.

All participants will have at least 24 hours (might have to increase this for difficult ethics committees to a week) to consider whether they wish to participate.

10 WITHDRAWAL OF STUDY PARTICIPANTS

Participants are free to withdraw from the study at any point. No attempt will be made to record reason for withdrawal. The participant will have the option of withdrawal from

- Ι. all aspects of the study but continued use of data collected up to that point
- П. all aspects of the study with removal of all previously collected data.

11 DATA COLLECTION

The data to be collected are the opinions of women (and their partners) and clinicians. These will include:

Phase 1 Survey results during the surveys we will collect no personal data (including IP addresses for the online surveys) unless the individual volunteers to provide contact information and requests to receive further information about phase 2 or 3 of the study. We will then request title, name, surname, address postcode, telephone and email contact details.

Phase 2 Discussion at the interactive consensus workshop (which will be audio-recorded (with consent) to aid future analysis) opinions will not be attributed to individuals. Audio recording will be held securely and transferred using a secure data transfer system i.e. Datasync. The data produced will be a ranking of scenarios (longlist and shortlist)

Phase 3 Data collected during the Focus groups and Interviews will be audio-recorded to aid future analysis. Audio recordings will transferred using the DataSync cloud service operated and hosted by the University of Edinburgh. Files on Datasync are only visible to others, if they are shared. Digital audio recordings of interviews will be uploaded to Datasync and an encrypted and time-limited link sent to a transcription company to enable the file to be downloaded. Transcripts of audio files will be returned to the researcher using password-encrypted word files. The transcription company will be asked to sign a confidentiality agreement, Only members of the research team will have access to the raw data or transcripts. At the point at which transcription takes place all information, which could potentially identify participants will be removed e.g. names, place names.

12 SOURCE DATA DOCUMENTATION

All data created for this study will be source there is no plan to access any pre-existing records or review medical notes. Participants will provide consent for the data obtained during the process.

Source data will be the surveys; electronic and paper. Audio recordings taken during the Delphi consensus, interviews and Focus groups will be transcribed and the transcriptions will be held as anonymised source data.

Further the output of the interactive working group will be a consensus summary, which will not attribute opinions to individuals.

The focus groups and interviews will be transcribed and analysed using a thematic approach. Nvivo software will be used to facilitate data coding and retrieval.

13 STATISTICS AND DATA ANALYSIS

13.1 SAMPLE SIZE CALCULATION

Our planned sample sizes are as follows:

- Clinician survey, n= 200
- Public survey, n= 200
- Interactive working group, n=40
- Focus groups with women, n=30-60
- Interviews with clinicians, n=25

There are no generally accepted guidelines for the optimal size to achieve a consensus in Delphi studies [44] however it is most important to obtain a sample with a broad range of experience and expertise. Approximately 40 participants will be recruited.

13.2 PROPOSED ANALYSES

The survey data will be used to determine current practice and public opinion. We will use a Likert scale 1-5 and analyse with appropriate non-parametric and/or parametric tests. Where more than 85% of individuals responding to the surveys agree on an answer to a clinical scenario, we will designate the scenario as having good agreement, and being accepted clinical practice. Where less than 50% agree on an answer, we will assume that there is significant uncertainty. Where 50-70% agree, we will designate the scenario as having moderate uncertainty. Where 70-85% agree, we will designate the scenario as having some uncertainty.

Data analysis for the Consensus. Delphi process will involve graphical summation of the scores indicating the whole groups' and individual participant groups' responses using the Delphi Manager. Participants will be asked to score each scenario using the Grading of Recommendations Assessment Development and Evaluations (GRADE) scale for Delphi processes (accessed online). Participants will be asked for example: 'How important is to include the following scenarios in a randomised trial of mode of delivery (caesarean/vaginal) for a preterm baby?' A pre-specified scale and criteria (Williamson, Altman et al. 2012)will be used for dropping and retaining items in the long-list created from the survey: scenarios with >70% participants scoring 7-9 and <30% scoring 1-3 would be included in subsequent rounds.

Data analysis for the qualitative research will be undertaken by highly experienced qualitative researchers with input from other members of the co-investigator team. Individual interviews will be read through repeatedly and cross-compared to identify issues and experiences which cut across different accounts (Strauss and Corbin 1990). Depending on emerging findings, interviews may also be analysed in clusters and cross compared according to the sites/NHS trusts to which clinicians belong, their clinical/professional roles, and questionnaire responses. A similar approach will be used for the focus groups discussions, with particular attention being paid to differences and similarities in the perspectives and views of women belonging to different cultural and religious groups and to those with prior experience of CS and vaginal delivery. In line with others' recommendations (Kitzinger 1994, Duggleby 2005, Wilkinson, Rees et al. 2007), careful attention will be also paid in the analysis to group interactions, including use of humour, as participants' (different) assumption can be revealed through the ways they challenge, question and support one another in the context of a group discussion (Kitzinger 1994). Team members will undertake separate analyses and write independent reports before meeting to discuss their interpretation of the data and reach agreement of key findings and themes which will then be used to inform development of a coding frame. Coded datasets will be subjected to further analyses to allow more nuanced interpretations of the data to be developed and identify illustrative quotations. Nvivo software will be used to support data coding and retrieval.

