5 STUDY PLAN

5.1 Phase 1: Survey of current practice (Months 1-4)

We will perform a survey of clinicians regarding current practice and opinion offering examples of key clinical scenarios of women presenting in preterm labour or undergoing planned preterm delivery. The purpose of this survey is to determine the opinions of clinicians (consultant obstetricians, consultant neonatologists and midwives working in units with neonatal intensive care facilities) on the optimal mode of delivery. The survey will focus on scenarios where there is maximum clinical uncertainty and will be piloted to determine completion rates, ease of completion, and identify any questions which are unclear to respondents.

We will use a standardised format (likely an electronic format on a tool such as Bristol Online survey), and present options in the form of tick boxes and/or ratings scales. We will be careful to vary our "agree" or "highest rating score" between caesarean section and vaginal delivery to avoid bias from "yeasayers" (Boynton and Greenhalgh 2004). We believe that a closed ended design is likely to be appropriate, but we will include a free text box for further

communication at the end of the questionnaire. If comments in the free text box suggest there are important controversies that we have not presented, we will consider issuing a further survey. A request for demographic information of the respondent (age band, clinical specialty, preterm birth specialist or not) will be included at the end of the survey.

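### The survey agreement bands in section 13.2 do not fit a two-mode question on a 1–5 scale, so the uncertainty label depends on how an answer is counted and can be wrong in either direction

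*Protocol*

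**What the plan says.** Section 13.2 gives the response scale: "We will use a Likert scale 1-5". It then fixes four bands on the percentage in agreement:

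- Good agreement, treated as accepted practice: "Where more than 85% of individuals responding to the surveys agree on an answer to a clinical scenario".
- The two middle bands: "Where 50-70% agree, we will designate the scenario as having moderate uncertainty. Where 70-85% agree, we will designate the scenario as having some uncertainty".
- The most uncertain band: "Where less than 50% agree on an answer, we will assume that there is significant uncertainty".

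Section 5.1 leaves the item format open. The survey will "present options in the form of tick boxes and/or ratings scales", and the favourable end of the scale will be alternated between the two modes of delivery. The same cut-offs apply whatever the format. Neither section says whether an answer means one of the five points, one side of the scale, or a two-way choice. Section 13.1 plans 200 respondents for the clinician survey. Under section 5.2 the list of uncertainties from the survey goes into a two-round Delphi.

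**The concern.** The primary objective (section 2.1.1) is to find the groups for whom the best planned mode of birth is uncertain. Opinion divided evenly between the two modes is a clear case of that, and one would expect it to receive the strongest uncertainty label. Whether it does depends on a choice that section 13.2 does not make. Under one way of counting, evenly divided opinion is under-labelled; under another, near-consensus is over-labelled. The bands are the survey's only numerical definition of uncertainty, and their labels would describe the scenarios passed to the Delphi.

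**Working it through.** The protocol derives no figure here, so there is none to reproduce. The check applies the section 13.2 bands to the share of the most common answer under each way of counting.

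**Inputs.** Cut-offs of 50%, 70% and 85% and the 1–5 scale come from section 13.2, n = 200 from section 13.1, and the two modes and open item format from section 5.1. The neutral share *u* is not given in the documents; it is assumed and varied from 0 to 20%.

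**1. Two answers.** If a proportion *p* chooses one mode, the larger share is max(*p*, 1 − *p*) ≥ 0.5. At n = 200 the minimum is 100/200 = 50%, so the band below 50% is empty. A 100:100 split is labelled *moderate*. So is 139:61, since 139/200 = 69.5%. With true opinion at 50:50, P(*significant*) = 0 and P(*moderate*) > 0.9999.

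**2. Three groups (caesarean / neutral / vaginal).** With neutral share *u* and lead *d* of the favoured mode, that mode's share is (1 − *u* + *d*)/2, which is below 50% only when *u* > *d*. For a true even split and n = 200, the exact multinomial probabilities are:

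| Assumed neutral share | Expected share for each mode | P(*significant*) | P(*moderate*) |
|---|---|---|---|
| 0% | 50% | 0 | >0.9999 |
| 2% | 49% | 0.17 | 0.83 |
| 5% | 47.5% | 0.48 | 0.52 |
| 10% | 45% | 0.82 | 0.18 |
| 20% | 40% | 0.995 | 0.005 |

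Few neutral replies therefore leave most evenly divided scenarios under-labelled; 10–20% neutral replies mostly remove the problem.

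**3. Five raw points compared with collapsed sides.** Percentages run from point 1 to point 5:

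| Distribution | Largest single point | Label by raw point | Larger side | Label when collapsed |
|---|---|---|---|---|
| 25/25/0/25/25 | 25% | significant | 50% | moderate |
| 50/0/0/0/50 | 50% | moderate | 50% | moderate |
| 10/40/0/40/10 | 40% | significant | 50% | moderate |
| 0/0/8/46/46 | 46% | significant | 92% | good agreement |

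The last row is the most serious: 46% + 46% = 92% favour one mode, yet counting raw points gives the most uncertain label.

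**4. Overlap at 70%.** 140/200 = 70% satisfies both middle bands. If true agreement is 70%, P(X = 140) under Binomial(200, 0.70) is 0.061, so this affects about 6% of such scenarios.

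**The case against.** The strongest reply is that section 13.2 names a five-point scale, not a two-way choice. On five raw points an even divide such as 25/25/0/25/25 does reach the top band. So does an even split in three groups with a moderate neutral share. If agreement instead means the share agreeing with one named mode, a true 50% gives a value below 50% with probability 0.47. This stands: a reader might infer that the top band can never be reached, and the documents do not support that.

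A reader might also infer that the top band merely counts people who decline to choose. That does not hold either. A midpoint reply can express individual equipoise, which sections 1.1 and 5.2 say the study is looking for, so it is reasonable for neutral replies to push a scenario towards uncertainty.

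A third tempting inference is that mislabelled scenarios are lost to the Delphi. Nothing in the protocol restricts the Delphi list to one band. *Moderate* and *some* are also uncertainty labels. Under section 5.2, Delphi participants can add scenarios and score each one afresh on importance and uncertainty together.

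Finally, collapsing rules are often left to an analysis plan or the piloted questionnaire. That would answer a complaint about missing detail. It does not answer this one, because the protocol itself fixes the cut-offs: whichever plain counting rule is later adopted, raw points or collapsed sides, they mislabel some recognisable pattern of opinion. The overlap at 70% is in the protocol's own text.

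**Conclusion.** The point holds as a mislabelling problem. On two-way items, an even split is always labelled *moderate*. On three groups this happens in 83% of surveys at 2% neutral, 52% at 5%, 18% at 10% and about 0.5% at 20%, with n = 200, a true even split and assumed neutral shares. On raw points, a 92% majority for one mode can be labelled *significant uncertainty*. The double label at 70% is real but small. The size in practice depends on the item format and the neutral share, neither of which the protocol fixes. The effect is on how survey uncertainty is described; exclusion of scenarios from the Delphi is not shown. It is worth correcting because the rule bears directly on the primary objective and the correction is nearly free.

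**What to change.** Amend section 13.2 as follows:

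1. Collapse the 1–5 scale to caesarean / no preference / vaginal, after re-aligning items whose direction was reversed.
2. Apply the bands to the percentage of all respondents, including those with no preference, who favour the more-favoured mode.
3. Make the limits non-overlapping, for example 50% to <70%, 70% to 85%, and >85%.
4. State that a near-even split between modes belongs in the highest uncertainty category. Merging the two bands below 70% is one way to do this without a new cut-off; it is an option, not a necessity.
5. Report the three percentages beside each label.

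With the merged version, 100/0/100 and 25/25/0/25/25 (each 50%) fall in the highest category, 0/0/8/46/46 (92%) is good agreement, and 140/200 has one label.

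The cost is a few sentences, with no new data or respondents. If the bands are merged, the labels are coarser: 100:100 and 139:61 still share one, and more scenarios carry the top label. The reported percentages keep the gradation.

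### The survey rule in 13.2 counts agreement on any answer, so shared neutrality can be labelled accepted practice and, on the literal reading, same-direction opinion can be labelled significant uncertainty

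*Protocol*

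**What the plan says.** Section 13.2 of the Protocol fixes the scale: "We will use a Likert scale 1-5 and analyse with appropriate non-parametric and/or parametric tests". It then fixes four bands and their labels:

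- Top band: "Where more than 85% of individuals responding to the surveys agree on an answer to a clinical scenario", the investigators will "designate the scenario as having good agreement, and being accepted clinical practice".
- "Where 70-85% agree, we will designate the scenario as having some uncertainty".
- "Where 50-70% agree, we will designate the scenario as having moderate uncertainty".
- Bottom band: "Where less than 50% agree on an answer, we will assume that there is significant uncertainty".

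The section does not define an answer, does not say whether adjacent points are merged, gives no scale anchors, and does not treat the midpoint separately.

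Section 5.1 leaves the format partly open, since the survey will "present options in the form of tick boxes and/or ratings scales". It also shows what the ends of a rating scale stand for: "We will be careful to vary our 'agree' or 'highest rating score' between caesarean section and vaginal delivery". The two poles are therefore the two modes of delivery.

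Section 5.2 says the survey's list of clinical uncertainties is what the two-round Delphi reduces to a short-list. Its description of round one takes it as likely that some scenarios will already have been dropped from the longlist. Section 3.1.2 lists the survey results as a secondary endpoint in their own right.

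**The concern.** The survey is meant to establish current practice and equipoise (section 5.2), and the primary objective (section 2.1.1) is to find the groups for whom the best planned mode of birth is uncertain. A share of identical answers does not measure that. It is high when respondents crowd on one answer, whatever the answer means, and low when they spread out, even if they spread over two strengths of the same opinion.

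Two errors can follow. A scenario in which nearly everyone has no preference can be reported as accepted practice, the opposite of what the study is looking for. A scenario in which nearly everyone prefers the same mode, with differing conviction, can be reported as highly uncertain. The labels shape the list of uncertainties taken to the Delphi, and they are reported as survey findings.

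**Working it through.** **Inputs.** Scale of 1 to 5 and the cut-offs 50%, 70% and 85% (section 13.2); 200 clinicians in the survey (section 13.1), used only to turn percentages into counts. The Protocol gives no figure to reproduce and no response data. The distributions below are assumptions chosen to show how the rule behaves.

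**Assumption on the anchors.** Points 1 and 2 favour one mode, 3 is neutral, and 4 and 5 favour the other mode.

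**Three ways to count agreement.** With p1 to p5 the shares at each point:

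- (a) Single point, the literal reading: max(p1, p2, p3, p4, p5).
- (b) Merged to three categories: max(p1+p2, p3, p4+p5).
- (c) Directional: max(p1+p2, p4+p5), with all respondents in the denominator.

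| Pattern, % at points 1-5 | Counts of 200 | (a) Single point | (b) Merged | (c) Directional |
|---|---|---|---|---|
| 0/6/88/6/0 | 0/12/176/12/0 | 88%: accepted practice | 88%: accepted practice | 6%: significant uncertainty |
| 45/45/10/0/0 | 90/90/20/0/0 | 45%: significant uncertainty | 90%: good agreement | 90%: good agreement |
| 49/49/2/0/0 | 98/98/4/0/0 | 49%: significant uncertainty | 98%: good agreement | 98%: good agreement |
| 60/40/0/0/0 | 120/80/0/0/0 | 60%: moderate uncertainty | 100%: good agreement | 100%: good agreement |
| 45/5/0/5/45 | 90/10/0/10/90 | 45%: significant uncertainty | 50%: moderate uncertainty | 50%: moderate uncertainty |

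**Neutral answers.** The first row is misread under (a) and under (b), because the neutral category is itself the most common answer. With a neutral share above 85%, the larger directional share is below 100 − 85 = 15%, yet the scenario gets the most settled label. The effect is graded. Where the midpoint is the commonest answer, a neutral share of 50-70% gives moderate uncertainty and 70-85% gives some uncertainty, so more neutrality produces a more settled label.

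**Same-direction answers.** Rows two and three are misread only under (a). Under (a), row two (90% on one side) and row five (evenly polarised) have the same largest share, 45%, and so the same label. Under (b) or (c) they separate: 90% against 50%.

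Only (c) removes both errors.

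**The case against.** The strongest reply is that the text does not commit to the reading that fails. An answer is undefined, the anchors are not given, tick boxes are allowed, and the questionnaire is to be piloted. If an answer means a mode of delivery, the same-direction error disappears. Anchors and merging rules are also often settled in the questionnaire or the statistical analysis plan, which are not at hand. This stands in part: the same-direction error is conditional on reading an answer as one of five points, and the neutral error is conditional on point 3 being neutral. It does not dispose of the point, because the Protocol itself fixes the scale, the cut-offs and the labels. The neutral error survives merging, and a no-preference tick box would reproduce it.

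A second reply is that the survey is only an early screen. Section 5.1 provides a free-text box and a possible further survey. In section 5.2, round one lets participants add scenarios, scoring combines importance with clinical uncertainty, and a final meeting reviews what was retained and dropped. These are real safeguards, and they soften the harm. They do not remove it: recovering a scenario already labelled accepted practice depends on someone raising it, and none of them corrects the survey result as reported.

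A reader might infer that the rule automatically strikes equipoise scenarios from the Delphi. The documents do not support that. Section 13.2 attaches labels; some pruning before the Delphi is implied, but no operating rule ties removal to a band. Nor do they show how often the errors would occur. Section 1.2 describes clinicians as holding opposed beliefs, which suggests divided opinion rather than near-unanimous neutrality.

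**Conclusion.** The point holds in conditional form. As written, the classification in 13.2 does not distinguish direction of preference from neutrality.

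- If the midpoint is neutral, more than 85% choosing it (at least 171 of 200, since 0.85 × 200 = 170) is labelled accepted clinical practice. This holds on the single-point and the merged reading.
- If an answer is a single scale point, 90% or even 98% favouring one mode can be labelled significant uncertainty. At 90%, in the 45/45 example, the largest share equals that of an evenly polarised scenario.

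The sizes rest on illustrative distributions, not on data or a forecast. The consequence is a possible mislabelling of survey results and of the list taken forward, softened by the later steps. Severity: should-fix. Confidence: medium, because the anchors and the meaning of an answer are unstated.

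**What to change.** Amend section 13.2 before the survey opens:

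- Recode every item to a common direction. Define agreement as the larger of two shares: all responses favouring caesarean section, or all responses favouring vaginal delivery. Keep all respondents in the denominator.
- State that neutral or unsure responses never count as agreement, and report their share separately as individual equipoise.
- Make sure each item, whether rating scale or tick box, offers a labelled neutral option.

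The 50/70/85% cut-offs can stay, and so can the variation of the high-score end in section 5.1, since recoding takes care of it.

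The cost is a short addition to 13.2, minor recoding and slightly less freedom in questionnaire format; no extra respondents are needed. One consequence should be accepted knowingly. With no neutral answers the larger directional share cannot fall below 50%, so an even split lands at the bottom of the moderate band. Printing both directional shares beside the neutral share for each scenario keeps that visible. Settling the definition in advance also avoids choosing how to merge categories after seeing the responses.
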